4.8 Management Guidelines for Immunotherapy (I-O) Agents

I-O agents are associated with irAEs that can differ in severity and duration from AEs caused by other therapeutic classes. Nivolumab and ipilimumab are considered I-O agents in this protocol.

Early recognition and management of irAEs may mitigate severe toxicity. Management algorithms have been developed from extensive experience with nivolumab and ipilimumab to assist investigators in assessing and managing the following groups of irAEs:

- Gastrointestinal
- Renal
- Pulmonary
- Hepatic
- Endocrinopathies
- Skin
- Neurological

The clinical nature of AEs noted with encorafenib and binimetonib will determine the role of the above algorithms for use in toxicities related to its use in this study. The algorithms recommended for utilization in this protocol are included in Appendix 2.

Table 4.2 Reference Adverse Events (AEs) and toxicity Management Guidelines

ADVERSE EVENTS	NIVOLUMAB	IPILIMUMAB	ENCORAFENIB	BINIMETINIB
DIARRHEA/COLITIS	X	X	X	X
ABNORMAL LIVER ENZYME TEST	X	X	X	X
SKIN RASH	X	X	X	X
SERIOUS SKIN REACTION	X	X	X	X
NEPHRITIS	X	X	X	X
PNEUMONITIS	X	X		
ENDOCRINE EVENTS	X	X	X	X
HAND FOOT SKIN REACTION	X	X	X	X
NEUTROPENIA AND THROMBOCYTOPENIA	X	X	X	X
ABNORMAL LABORATORY RELATED AES	X	X	X	X
ASYMPTOMATIC AMYLASE/LIPASE ELEVATION	X	X	X	X
INFUSION REACTION AND CYTOKINE RELEASE SYNDROME	X			
LVEF			X	X
HYPERTENSION			X	X
NEW MALIGNANCIES			X	X
PYREXIA			X	X
VISUAL CHANGES			X	X
HYPERGLYCEMIA			X	X
HEMORRHAGE			X	X
THROMBOTIC EVENTS				X

*X indicates study treatment that may need to be modified

4.9 Management Guidelines for Targeted Therapy

See Appendix 2 and 3.

4.10 Guidelines for Permanent Discontinuation

- Any Grade 2 drug-related uveitis or eye pain or blurred vision that does not respond to topical therapy and does not improve to Grade 1 severity within the re-treatment period OR requires systemic treatment
- Any Grade 3 non-skin, drug-related AE lasting > 7 days, with the following exceptions for laboratory abnormalities, drug-related uveitis, pneumonitis, bronchospasm, hypersensitivity reactions, infusion reactions, and endocrinopathies:
 - Grade 3 drug-related uveitis, pneumonitis, bronchospasm, hypersensitivity reaction, or infusion reaction of any duration requires discontinuation
 - Grade 3 drug-related endocrinopathies adequately controlled with only physiologic hormone replacement do not require discontinuation
 - Grade 3 drug-related laboratory abnormalities do not require treatment discontinuation except:
 - ◆ Grade 3 drug-related thrombocytopenia > 7 days or associated with bleeding requires discontinuation
- Any drug-related liver function test (LFT) abnormality that meets the following criteria require discontinuation:
 - AST or ALT > 8 x ULN
 - Total bilirubin > 5 x ULN
 - Concurrent AST or ALT > 3 x ULN and total bilirubin > 2 x ULN
- Any Grade 4 drug-related AE or laboratory abnormality, except for the following events which do not require discontinuation:
 - Grade 4 neutropenia ≤ 7 days
 - Grade 4 lymphopenia or leukopenia
 - Isolated Grade 4 amylase or lipase abnormalities that are not associated with symptoms or clinical manifestations of pancreatitis. The Study PI should be consulted for Grade 4 amylase or lipase abnormalities.
 - Isolated Grade 4 electrolyte imbalances/abnormalities that are not associated with clinical sequelae and are corrected with supplementation/appropriate management within 72 hours of their onset

Phase I/II study of encorafenib and binimetinib with nivolumab and low dose ipilimumab in metastatic *BRAF* mutant melanoma

- Any event that leads to delay in dosing lasting > 6 weeks from the previous dose requires discontinuation, with the following exceptions:
 - Dosing delays to allow for prolonged steroid tapers to manage drug-related AEs are allowed. Prior to re-initiating treatment in a subject with a dosing delay lasting > 6 weeks from the previous dose, the Study PI must be consulted. Tumor assessments should continue as per protocol even if dosing is delayed. Periodic study visits to assess safety and laboratory studies should also continue every 6 weeks or more frequently if clinically indicated during such dosing delays.
 - Dosing delays lasting > 6 weeks from the previous dose that occur for non-drug-related reasons may be allowed if approved by the Study PI. Prior to re-initiating treatment in a subject with a dosing delay lasting > 6 weeks, the Study PI must be consulted. Tumor assessments should continue as per protocol even if dosing is delayed. Periodic study visits to assess safety and laboratory studies should also continue every 6 weeks or more frequently if clinically indicated during such dosing delays.

- Any AE, laboratory abnormality, or intercurrent illness which, in the judgment of the Investigator, presents a substantial clinical risk to the subject with continued nivolumab or ipilimumab dosing.

Note: If a subject experiences a severe AE during induction treatment (ie, the combination of nivolumab and ipilimumab) that requires discontinuation from further treatment with the combination, continuing treatment with nivolumab monotherapy may be considered contingent on discussion with and approval by the Study PI.

Exceptions to Permanent Discontinuation of study drug dosing under the following situations:

- Potentially reversible inflammation (< Grade 4), attributable to a local anti-tumor reaction and a potential therapeutic response. This includes inflammatory reactions at sites of tumor resections or in draining lymph nodes, or at sites suspicious for, but not diagnostic of metastasis.
- Participants with the following conditions where in the investigator's opinion continuing study drug administration is justified:
 - Endocrinopathies where clinical symptoms are controlled with appropriate hormone replacement therapy.

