APPENDIX 2 DOSE REDUCTION FOR ENCORAFAENIB RELATED ADVERSE EVENTS

Action	Recommended Dose
First Dose Reduction	300mg (four 75mg capsules) PO once daily
Second Dose Reduction	225mg (three 75mg capsules) PO once daily
Third Dose Reduction	150mg (two 75mg capsules) PO once daily
Subsequent Modification	Discontinue

Severity of Adverse Event	Dose Modification
New Primary Malignancies	
Non-cutaneous RAS positive malignancies	Permanently Discontinue
Uveitis	
Grade 1–3	If Grade 1 or 2 does not respond to specific ocular therapy, or for Grade 3 uveitis, withhold encorafenib and binimetinib for up to 6 weeks. 
• If improved, resume at same or reduced dose.• If not improved, permanently discontinue.
Grade 4	Permanently discontinue encorafenib and binimetinib.
Other Eye Disorders (i.e., non-Uveitis Events)	

Severity of Adverse Event	Dose Modification
Grade 1–2	Maintain dose level of encorafenib and binimetonib and increase frequency of ophthalmic monitoring to at least every 14 days until stabilization or resolution.
Grade 3	Interrupt dosing of encorafenib and binimetonib and refer patient to ophthalmologist within 7 days.
	
 1. If resolved to Grade \leq 1 in \leq 21 days, resume treatment at 1 reduced dose level of encorafenib and binimetonib. 2. If not resolved to Grade \leq 1 in \leq 21 days, permanently discontinue encorafenib and binimetonib and close follow-up with ophthalmic monitoring until stabilization or resolution.
Grade 4	Permanently discontinue encorafenib and binimetonib and immediate follow-up with ophthalmic monitoring until stabilization or resolution.
QTc Prolongation	
QTcF $>$ 500 ms and \leq 60 ms increase from baseline	
1st occurrence:
 
 • Temporarily interrupt dosing of encorafenib until QTcF $<$ 500 ms. Then resume treatment at 1 reduced dose level of encorafenib. 
2nd occurrence:
 
 • Temporarily interrupt dosing of encorafenib treatment until QTcF $<$ 500 ms. Then resume treatment at 1 reduced dose level of encorafenib. 
3rd occurrence:
 
 • Permanently discontinue encorafenib.
QTcF $>$ 500 ms and $>$ 60 ms increase from baseline	Permanently discontinue.

Severity of Adverse Event	Dose Modification
Dermatologic (Except Hand-foot Skin Reactions)	

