APPENDIX 3 DOSE REDUCTION FOR BINIMETINIB RELATED ADVERSE EVENTS

Action	Recommended Dose
First Dose Reduction	30mg PO BID
Subsequent Modification	Discontinue

Severity of Adverse Event	Dose Modification
Cardiomyopathy	
Asymptomatic, absolute decrease in LVEF of > 10% from baseline that is also below the LLN	Withhold binimetinib for up to 4 weeks, evaluate LVEF every 2 weeks. Resume binimetinib at a reduced dose if the following are present: 
 • LVEF is at or above the LLN and • Absolute decrease from baseline is 10% or less and • Patient is asymptomatic. If LVEF does not recover within 4 weeks permanently discontinue binimetinib
Grade 3–4 (Symptomatic congestive heart failure or absolute decrease in LVEF of > 20% from baseline that is also below LLN)	Permanently discontinue binimetinib. Closely monitor LVEF until resolution or up to 16 weeks.
Venous Thromboembolism	
Uncomplicated DVT or PE	Withhold binimetinib. 
 • If improves to Grade 0–1, resume at a reduced dose. • If no improvement, permanently discontinue binimetinib. Permanently discontinue encorafenib and binimetinib.
Life Threatening PE	
Serous Retinopathy	

Severity of Adverse Event	Dose Modification
Symptomatic serous retinopathy/ Retinal pigment epithelial detachments	
Withhold binimetinib for up to 10 days.
 
 • If improves and becomes asymptomatic, resume at the same dose. • If not improved, resume at a lower dose level or permanently discontinue binimetinib
Retinal Vein Occlusion (RVO)	
Any Grade	Permanently discontinue binimetinib.
Uveitis	
Grade 1–3	
If Grade 1 or 2 does not respond to specific ocular therapy, or for Grade 3 uveitis, withhold binimetinib and encorafenib for up to 6 weeks.
 
 • If improved, resume at same or reduced dose. • If not improved, permanently discontinue binimetinib
Grade 4	Permanently Discontinue
Other Eye Disorders (i.e., Non-retinal Events, non-Uveitis Events)	

Severity of Adverse Event	Dose Modification
Grade 1–2	Maintain dose level of encorafenib and binimetinib and increase frequency of ophthalmic monitoring to at least every 14 days until stabilization or resolution.

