Grade 3	Interrupt dosing of encorafenib and binimetinib and refer patient to ophthalmologist within 7 days. 
 • If resolved to Grade ≤ 1 in ≤ 21 days, resume treatment at 1 reduced dose level of encorafenib and binimetinib. • If not resolved to Grade ≤ 1 in ≤ 21 days, permanently discontinue encorafenib and binimetinib and close follow-up with ophthalmic monitoring until stabilization or resolution
Grade 4	Permanently discontinue encorafenib and binimetinib and immediate follow-up with ophthalmic monitoring until stabilization or resolution.
Interstitial Lung Disease	
Grade 2	Withhold binimetinib for up to 4 weeks. 
 • If improved to Grade 0–1, resume at a reduced dose. • If not resolved within 4 weeks, permanently discontinue
Grade 3 or Grade 4	Permanently discontinue
Rhabdomyolysis or Creatine Phosphokinase (CPK) elevations	
Grade 4 asymptomatic CPK elevation or Any Grade CPK elevation with symptoms or with renal impairment	Withhold binimetinib dose for up to 4 weeks. 
 • If improved to Grade 0–1 resume at a reduced dose. • If not resolved within 4 weeks, permanently discontinue binimetinib

Severity of Adverse Event	Dose Modification
Dermatologic	
Grade 2	If no improvement within 2 weeks, withhold until Grade 0–1. Resume at same dose if first occurrence or reduce dose if recurrent.
Grade 3	Withhold until Grade 0–1. Resume at same dose if first occurrence or reduce dose if recurrent.
Grade 4	Permanently discontinue
Nausea/Vomiting	
Grade 1–2	Maintain dose level of encorafenib and binimatinib. Promptly institute antiemetic measure.
Grade 3	Interrupt dosing of encorafenib and binimatinib until resolved to Grade \leq 1. Then resume treatment at 1 reduced dose level of encorafenib. Resume treatment with binimatinib at the current dose if, in the judgment of the Investigator, the toxicity is considered to be unrelated to binimatinib, or at 1 reduced dose level. Note: Interrupt dosing of encorafenib and binimatinib for \geq Grade 3 vomiting or Grade 3 nausea only if the vomiting or nausea cannot be controlled with optimal antiemetics (as per local practice).
Grade 4	Permanently discontinue encorafenib and binimatinib
Other Adverse Reactions (including hemorrhage)	

Severity of Adverse Event	Dose Modification

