Recurrent Grade 2 or First occurrence of any Grade 3	Withhold for up to 4 weeks. 
 • If improves to Grade 0–1 or to pretreatment/baseline levels, resume at reduced dose. • If no improvement, permanently discontinue.
First occurrence any Grade 4	Permanently discontinue or withhold for up to 4 weeks. 
 • If improves to Grade 0–1 or to pretreatment/baseline levels, then resume at a reduced dose. • If no improvement, permanently discontinue.
Recurrent Grade 3	Consider permanently discontinuing.
Recurrent Grade 4	Permanently discontinue participants

**APPENDIX 4 COMMON TERMINOLOGY CRITERIA FOR ADVERSE EVENTS
V5.0 (CTCAE)**

The descriptions and grading scales found in the revised NCI Common Terminology Criteria for Adverse Events (CTCAE) version 5.0 will be utilized for AE reporting.
(<http://ctep.cancer.gov/reporting/ctc.html>)

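### Section 4.10 does not say which of the four drugs its permanent stops cover; read as written, it contradicts the hold-and-resume rows of Appendices 2 and 3 for four kinds of event

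*Combined protocol and SAP*

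**What the plan says.** Section 4.10 (Guidelines for Permanent Discontinuation) is worded for drug-related events in general. On Grade 3 eye and immune-type events it says "Grade 3 drug-related uveitis, pneumonitis, bronchospasm, hypersensitivity reaction, or infusion reaction of any duration requires discontinuation". It also stops treatment for Grade 3 non-skin events lasting more than 7 days, with listed exceptions that include most laboratory abnormalities. For the highest grade the rule is "Any Grade 4 drug-related AE or laboratory abnormality, except for the following events which do not require discontinuation". Four exceptions follow: short neutropenia, lymphopenia or leukopenia, isolated amylase or lipase, and corrected electrolytes. CPK is not among them.

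Section 4.9, on targeted therapy, only points to Appendices 2 and 3. On uveitis, Appendix 2 says "or for Grade 3 uveitis, withhold encorafenib and binimetinib for up to 6 weeks" and then "If improved, resume at same or reduced dose". Appendix 3 says "or for Grade 3 uveitis, withhold binimetinib and encorafenib for up to 6 weeks", again with resumption if improved. In Appendix 3 the row for "Grade 4 asymptomatic CPK elevation or Any Grade CPK elevation with symptoms or with renal impairment" reads "Withhold binimetinib dose for up to 4 weeks", with resumption at a reduced dose on recovery to Grade 0–1. For a first occurrence of any other Grade 4 reaction it reads "Permanently discontinue or withhold for up to 4 weeks".

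No section says whether 4.10 or the appendices take precedence.

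**The concern.** Section 4.10 and the appendices can both be opened for the same event in the same patient. If 4.10 covers all study drugs, a site that follows an appendix may re-dose encorafenib or binimetinib in a patient whom 4.10 stops permanently. If 4.10 covers only the antibodies, a site that reads it literally will stop oral drugs that the appendices would have resumed.

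Patient safety is the main stake. There is a secondary route to the primary endpoint. Under Section 4.7, failing to tolerate 66% of the planned encorafenib (with or without binimetinib) dose is itself a DLT, so a page-dependent stop could in principle change a patient's DLT status.

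**Working it through.** **Step 1. The texts side by side.** The plan gives no figure for this point, so the check is a row-by-row comparison.

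| Event | Section 4.10 as written | Appendices | Result |
|---|---|---|---|
| Grade 3 uveitis | Stop, any duration | 2 and 3: hold up to 6 weeks, resume at same or reduced dose if improved | Direct conflict, both oral drugs |
| Grade 3 other eye disorder, > 7 days, Grade ≤ 1 by day 21 | Stop | 2 and 3: resume one level lower | Direct conflict, both oral drugs |
| Grade 4 asymptomatic CPK | Stop (not an exception) | 3: hold up to 4 weeks, resume reduced | Direct conflict, binimetinib |
| Other first Grade 3 reaction, non-skin and non-laboratory, > 7 days, improved within 4 weeks | Stop | 3: resume reduced | Direct conflict, binimetinib |
| First other Grade 4 | Stop | 3: stop, or hold and resume | Partial: stopping satisfies both |

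The CPK and other-reactions rows appear only in the binimetinib appendix. They therefore do not touch the triple cohort, which receives no binimetinib.

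**Step 2. Does any text limit 4.10 to one drug class?**
- Sections 4.8 (immunotherapy), 4.9 (targeted therapy) and 4.11 (nivolumab or ipilimumab) name their class in the title. Section 4.10 does not.
- The exceptions in 4.10 refer to study drug dosing, and Table 4.1 lists all four agents as study drugs.
- Section 4.10 covers blurred vision. Table 4.2 assigns visual changes to encorafenib and binimetinib only.
- Section 3.5 sends the reader to a Section 4.3.5 for further reasons to discontinue. No such section appears in the document.
- Section 4.8 places its recommended algorithms in Appendix 2, which is the encorafenib table. The immunotherapy algorithms are in Appendix 6.

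**Step 3. Which of these events are already DLTs under Section 4.7?** Grade 4 CPK falls under the catch-all for any other Grade ≥ 3 event, so it is a DLT whichever page is followed. The same holds for most other Grade 3 and Grade 4 reactions. Some Grade 3 events have their own duration limits that a > 7-day event already exceeds or has reached: diarrhoea > 5 days, nausea and vomiting > 3 days, hypertension > 7 days. What can escape is mainly a Grade 3 other eye disorder (a DLT only after > 21 days) or a Grade 3 immune-related event (a DLT only after > 14 days). Uveitis has no named row and could be placed under either.

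**Step 4. The 66% clause for those remaining cases.** Assume that Cycle 1 is the 6-week window.
- Dosing days needed: 0.66 × 42 = 27.7, so 28.
- Permanent stop after 14 days: 14/42 = 33%. After 21 days: 21/42 = 50%. After 27 days: 27/42 = 64%. All are below 66%. After 28 days: 28/42 = 67%, so a later stop makes no difference.
- Hold of 14 days, then the same dose: (42 − 14)/42 = 67%, above the limit. A longer hold inside the window falls below it.
- The other-eye row resumes at a reduced level. In the quadruple cohort that is 300/450 = 67% and 30/45 = 67% of dose. If the clause is counted in mg, with d full-dose days before a hold of h days, the condition is d + (2/3)(42 − d − h) ≥ 27.72, which gives h ≤ d/2 + 0.42. An 8-day hold then needs d ≥ 15.2, that is 16 or more full-dose days before onset.

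**Step 5. What one reclassified patient would do.** One in 12 is 8.3 points. The exact one-sided upper 90% bound is the 0.90 quantile of Beta(x + 1, 12 − x). It gives 55.9% (4/12), 63.8% (5/12), 71.2% (6/12) and 78.1% (7/12), which reproduces 56, 64, 71 and 78 in Table 8.1. Going from 6 to 7 DLTs crosses the 75% safety limit in the Synopsis. Going from 7/12 (58%) to 8/12 (67%) crosses the < 60% criterion in Section 8.

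**The case against.** The strongest defence is that 4.10 is meant for nivolumab and ipilimumab only. One of its bullets names those two drugs, and a note discusses continuing nivolumab alone after the combination is stopped. Its six-week delay rule, counted from the previous dose, suits infusions better than daily tablets. Section 4.9 sends targeted therapy to the appendices. Section 3.5 makes stopping mandatory for investigational product and leaves non-investigational product, which here means encorafenib and binimetinib, to the investigator. On this reading a patient with Grade 3 uveitis stops the antibodies and may resume the oral drugs, and both texts are obeyed.

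This reading is plausible but nowhere stated, and Step 2 shows text pointing the other way. Discretion in 3.5 does not reconcile the pages; it adds a third standard. Section 4.7 lets one class be held while the other continues, but that sentence concerns dose delay. Even if the defence is right, a scope statement is missing.

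Four stronger readings are tempting and should not be made:
- That every event in the quoted sentence conflicts. Only uveitis has a directly opposing named row. Grade 3 pneumonitis agrees with the interstitial lung disease row of Appendix 3, and infusion reactions concern the antibodies.
- That a first other Grade 4 event gets opposite instructions. Appendix 3 allows permanent discontinuation.
- That patients would be restarted on a drug that must never be restarted. This presumes that 4.10 governs the oral drugs, which is the open question.
- That the conflict broadly shifts DLT rates. Most of the events are DLTs under 4.7 on either page.

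**Conclusion.** The inconsistency is real on the face of the text. There are four direct conflicts, two affecting both oral drugs and two affecting binimetinib only, plus one partial conflict. The whole conflict concerns re-dosing of encorafenib and binimetinib; the appendices do not direct a restart of nivolumab or ipilimumab. If 4.10 was meant for the antibodies alone, the defect shrinks to a missing scope sentence, and the same amendment is still needed.

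The main consequence is that the same patient may be stopped permanently or re-dosed. The effect on the primary endpoint is possible but narrow. It is confined mainly to Grade 3 eye events that are not DLTs by their own row, with onset before 28 dosing days and a hold of about 14 days or less; it is narrower still if dose is counted in mg after a reduction. It assumes that Cycle 1 is the 42-day window and that the patient is counted as a DLT rather than dropped as non-evaluable, since 4.7 uses the same 66% for evaluability. The documents give no frequency for these events, so 8.3 points per reclassified patient is the size of one case, not an expected bias.

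**What to change.** Reconcile Section 4.10 with Appendices 2 and 3 in one amendment:
- state for each 4.10 bullet which of the four drugs it governs;
- state which text takes precedence when an event cannot be attributed to one drug class;
- give one instruction per drug for Grade 3 uveitis, Grade 3 other eye disorders, Grade 4 asymptomatic CPK, other first Grade 3 reactions lasting > 7 days, and first other Grade 4 events;
- correct the pointer in 3.5 to Section 4.3.5 and the pointer in 4.8 to Appendix 2.

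Which clinical instruction is kept is for the sponsor and investigators to decide. The cost is amendment wording and a site memo, with no added procedures or patients.

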4.11 Treatment of Nivolumab or Ipilimumab Related Infusion Reactions

Since nivolumab and ipilimumab contain only human immunoglobulin protein sequences, it is unlikely to be immunogenic and induce infusion or hypersensitivity reactions. However, if such a reaction were to occur, it might manifest with fever, chills, rigors, headache, rash, pruritus, arthralgias, hypotension, hypertension, bronchospasm, or other allergic-like reactions. All Grade 3 or 4 infusion reactions should be reported

within 24 hours to the study medical monitor and reported as an SAE if it meets the criteria. Infusion reactions should be graded according to NCI CTCAE (Version 5.0) guidelines.

Treatment recommendations are provided below and may be modified based on local treatment standards and guidelines, as appropriate:

For Grade 1 symptoms: (mild reaction; infusion interruption not indicated; intervention not indicated):

- Remain at bedside and monitor subject until recovery from symptoms. The following prophylactic premedications are recommended for future infusions: diphenhydramine 50 mg (or equivalent) and/or acetaminophen/paracetamol 325 to 1000 mg at least 30minutes before additional nivolumab administrations.

For Grade 2 symptoms: (moderate reaction requires therapy or infusion interruption but responds promptly to symptomatic treatment (eg, antihistamines, non-steroidal anti-inflammatory drugs, narcotics, corticosteroids, bronchodilators, IV fluids); prophylactic medications indicated for <24 hours):

Stop the nivolumab or ipilimumab infusion, begin an IV infusion of normal saline, and treat the subject with diphenhydramine 50 mg IV (or equivalent) and/or acetaminophen/paracetamol 325 to 1000mg; remain at bedside and monitor subject until resolution of symptoms. Corticosteroid and/or bronchodilator therapy may also be administered as appropriate. If the infusion is interrupted, then restart the infusion at 50% of the original infusion rate when symptoms resolve; if no further complications ensue after 30 minutes, the rate may be increased to 100% of the original infusion rate. Monitor subject closely. If symptoms recur, then no further BMS-936558 will be administered at that visit.

- For future infusions, the following prophylactic premedications are recommended: diphenhydramine 50 mg (or equivalent) and/or acetaminophen/paracetamol 325 to 1000 mg should be administered at least 30 minutes before nivolumab infusions. If necessary, corticosteroids (up to 25 mg of SoluCortef or equivalent) may be used.

For Grade 3 or 4 symptoms: (severe reaction, Grade 3: prolonged [ie, not rapidly responsive to symptomatic medication and/or brief interruption of infusion]; recurrence of symptoms following initial improvement; hospitalization indicated for other clinical sequelae (eg, renal impairment, pulmonary infiltrates). Grade 4: Life-threatening; pressor or ventilatory support indicated):

- Immediately discontinue infusion of nivolumab or ipilimumab. Begin an IV infusion of normal saline and treat the subject as follows: Recommend bronchodilators, epinephrine 0.2 to 1 mg of a 1:1000 solution for subcutaneous administration or 0.1 to 0.25 mg of a 1:10,000 solution injected slowly f or IV administration, and/or diphenhydramine 50 mg IV with methylprednisolone 100 mg IV (or equivalent), as needed. Subject should be monitored until the Investigator is comfortable that the symptoms will not recur. Nivolumab or ipilimumab will be permanently discontinued. Investigators should follow their institutional guidelines for the treatment of anaphylaxis. Remain at bedside and monitor subject until recovery of the symptoms.

In case of late-occurring hypersensitivity symptoms (eg, appearance of a localized or generalized pruritus within 1 week after treatment), symptomatic treatment may be given (eg, oral antihistamine or corticosteroids).

